### 1.2 RATIONALE FOR STUDY

A non-commercial computational model has been developed in-house to estimate the patient's anterior-posterior or lateral depth using the radiographic image and the known exposure factors with which it was undertaken. This model has been tested using single composition phantoms and found to be accurate. If it was found to be accurate for real clinical examinations, this would automate the measurement of patient size and give local institutions the additional estimate of patient size required for local patient dose audit. In turn, this would provide the national data required to propose national reference values for paediatric x-ray examinations, which would give all local institutions an important comparator for their performance. This would lead to optimisation in those sites most requiring it; nationally, paediatric x-ray imaging would improve in time.

This pilot study is necessary to determine if the computational model is accurate enough to be relied upon.

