## 2. STUDY OBJECTIVES

### 2.1 OBJECTIVES

#### 2.1.1 Primary Objective

To determine how accurate the computational model is at determining the patient's anterior-posterior abdomen depth using the radiographic image and the known exposure factors with which it was acquired. Accuracy will be determined by comparing this result with an actual measurement of the patient's anterior-posterior abdomen depth made at the time of the examination.

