## **2.1.2 Secondary Objectives**

Any systematic inaccuracy found in the study could be used to further improve the values used in the computational model.

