### **2.2.2 Secondary Outcomes**

Any identified systematic inaccuracy could be used to further improve the values used in the computational model.

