## **3. STUDY DESIGN**

### **3.1 STUDY DESCRIPTION**

Willing volunteers will be found from patients who have been referred for an AP abdomen x-ray examination in the Radiology department at Ninewells Hospital. Any patient suffering severe abdominal pain when attending for the examination will be excluded as it will be necessary for light physical contact to be made with the patient's abdomen. Any patient that has had an injection of contrast media within the previous 24 hours will be excluded from the study as the computational model is not equipped to work with the presence of contrast media at present.

When the patient reports to main reception, if their attendance is for an AP abdomen x-ray the receptionist will give them the PIS and a reply slip saying that if they wish to take part in the study after having read the PIS they should inform the receptionist. The receptionist will then contact the PI who will be in the radiology department.

When it is time for the volunteer's examination, a radiographer will collect them from the waiting area as normal and bring them to the x-ray room as normal. Their examination will be performed on the Fuji Digital Radiography mobile x-ray machine in room D of main radiology at Ninewells Hospital.

Each patient will be assigned a unique numerical study ID that will be used to correlate the measurement of their anterior-posterior depth with their anonymised image.

The patient will lie on the x-ray couch in room D in the examination position, as directed by the radiographic staff. A measurement of the patient's AP abdomen depth will be made using a device that will attach to the side of the x-ray couch. This device is non-commercial and made in-house. It is not CE marked. Physical contact with the patient will be minimal; a wooden bar will rest gently on their abdomen. This will allow the AP abdomen depth to be read on the scale that is affixed to the x-ray couch.

This measurement will be recorded alongside the clinical indication for the patient under an anonymous and unique participant ID on a patient study form.

The AP abdominal x-ray examination will be undertaken by radiographic staff in accordance with local protocol and with no influence from this study. On completion, the patient's x-ray image will be transferred to PACS as normal, where it will be available for radiologist reporting. The patient will leave the department as normal with no additional request made of them for this study.

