### **8.2 PROPOSED ANALYSES**

Analyses is straightforward; the difference between the computationally predicted AP abdomen depth and that measured for each individual participant will be expressed as a percentage. Some statistical analyses will be undertaken on the 20 individual results (average, median, minimum and maximum deviations). A t-test will be used to compare predicted and measured results.

All analyses will be undertaken by the principal investigator using Microsoft Excel and IBM SPSS.

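### Section 8.2 never sets the deviations against the exposure factors that feed the model, so the planned analysis cannot show whether an error is tied to a setting, which limits the secondary objective.

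*Combined protocol and SAP*

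**What the plan says.** Section 8.2 (Proposed Analyses) starts from one figure per patient: "the difference between the computationally predicted AP abdomen depth and that measured for each individual participant will be expressed as a percentage". It then gives the summaries: "Some statistical analyses will be undertaken on the 20 individual results (average, median, minimum and maximum deviations". It ends with one test: "A t-test will be used to compare predicted and measured results". No section plans a plot, regression, correlation or breakdown of the deviations by any variable.

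Section 2.1.1 (Primary Objective) says that the model estimates depth "using the radiographic image and the known exposure factors with which it was acquired", and section 1.2 (Rationale) says the same. Section 3.1 (Study Description) has the examination done "in accordance with local protocol and with no influence from this study".

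Section 2.1.2 (Secondary Objectives) reads: "Any systematic inaccuracy found in the study could be used to further improve the values used in the computational model". Section 2.2.2 (Secondary Outcomes) repeats this almost word for word and names no analysis.

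Section 7.1 (Data Collection) lists sex, clinical indication and measured depth for the study form. It does not list the exposure factors.

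**The concern.** The model turns an image and its exposure factors into a depth. If one of its internal values is wrong only at some settings, the error appears only in patients imaged at those settings. Pooling all 20 deviations then does one of two things. If a single setting is affected, the average is diluted. If two settings err in opposite directions, the errors offset each other in the average and the t-test, and remain only as extra scatter.

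The secondary objective needs more than a net offset. To decide which value in the model to change, the investigator has to know what the error varies with, and the planned summaries do not provide that. The information needed is already held, because the model cannot be run without the exposure factors.

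**Working it through.** **Is there a figure in the plan to reproduce?** No. Section 8.1 states that the sample size of 20 has no statistical derivation. The plan gives no SD, effect size, significance level or accuracy limit. The check is therefore a reading of all sections, which confirms the omission, followed by an illustration.

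**Inputs from the documents.** n = 20; pooled average, median, minimum, maximum and one t-test (8.1, 8.2). Exposure factors are model inputs (1.2, 2.1.1).

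**Inputs assumed (not in the documents).** Effective attenuation 0.2 per cm (range 0.15 to 0.25); mean depth 22 cm; a 20% error in the model's output value at a setting; two settings; other scatter with SD 1, 1.5 or 2 cm; two-sided 5% level; the t-test taken as paired, since section 8.2 does not give its form.

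**Step 1: size of the error in depth.** Shift = ln(1.2)/attenuation.
- At 0.2 per cm: 0.1823/0.2 = 0.91 cm, or 0.91/22 = 4.1%.
- At 0.25 per cm: 0.73 cm (3.3%). At 0.15 per cm: 1.22 cm (5.5%).

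**Step 2: detection.** 40,000 simulated studies of 20 patients, shift 0.91 cm. The pooled test is a one-sample t-test on the deviations; the comparison is a two-sample t-test between settings.

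| Scenario | SD (cm) | Pooled t-test | Comparison by setting |
|---|---|---|---|
| Opposite errors, 10/10 | 1 | 1% | 97% |
| Opposite errors, 10/10 | 1.5 | 2% | 73% |
| Opposite errors, 10/10 | 2 | 3% | 49% |
| One setting wrong, 10/10 | 1 | 41% | 49% |
| One setting wrong, 10/10 | 2 | 15% | 16% |
| Opposite errors, 16/4 | 1 | 45% | 87% |
| Error only in the larger group, 16/4 | 1 | 84% | 34% |

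Over the attenuation range, the 97% runs from 87% (0.25 per cm) to 99.9% (0.15 per cm). In the opposite-error 10/10 rows the pooled test falls below its nominal 5% because the gap between settings inflates the SD.

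**Step 3: what a pooled average shows when one of two equal groups is wrong.** The mean deviation is 0.91/2 = 0.46 cm. If that average were used as the correction, it would leave 0.91 − 0.46, about +0.46 cm, in one half and 0 − 0.46 = −0.46 cm in the other.

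**Step 4: what the minimum and maximum show.** With opposite errors, 10/10 and SD 1 cm, they average about −11% and +11%, against −8.5% and +8.5% with no error. The extra spread is visible, but its source is not.

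**Step 5: what 20 patients can detect for a continuous factor.** Fisher z approximation: r = tanh[(1.96 + 0.84)/√(20 − 3)] = tanh(0.68) = 0.59 for 80% power, and about 0.66 for 90%.

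**The case against.** The strongest reply is that the pilot's answer does not rest on the pooled mean. Section 8.1 bases confidence on most or all results being accurate one by one, and section 8.2 begins with each patient's own percentage deviation. Those do not cancel, and nor do the minimum and maximum. This stands. A reader might infer that offsetting errors would lead the pilot to declare an inaccurate model accurate, or free of systematic error. The documents do not support that: only the average, the t-test and largely the median are affected.

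Second, nothing says that settings vary. Section 3.1 specifies one machine, one room and one projection under local protocol, and section 4.2 restricts entry to patients over 16. This also stands. If all patients have the same settings, the omission costs nothing.

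Third, 1% against 97% is the favourable case. The table bears this out: with one wrong setting detection hardly improves, and with a 16/4 split and the error in the larger group the pooled test does better.

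Fourth, an association with mAs may reflect patient size and would not by itself identify the value to change. This stands and shapes the fix.

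Fifth, the secondary objective is permissive, and no section says that the pooled average would be used as a correction. Step 3 therefore shows what such a correction would do, not what the plan intends. Exploration after the fact would also remain possible.

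What the reply leaves untouched is that no planned analysis serves the secondary objective beyond a net offset, although the data to do better must be in hand.

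**Conclusion.** The point holds as a limit on the secondary objective. Section 8.2 can reveal a net offset and the overall spread, but cannot show whether an error is tied to an exposure setting. The primary comparison is not invalidated.

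The size depends on unstated facts. With no variation in settings it is nil. With two equally used settings and opposite errors of 0.91 cm, the pooled t-test misses nearly all of what a comparison by setting finds at SD 1 cm (1% against 97%) and much of it at SD 2 cm (3% against 49%). With one wrong setting (41% against 49% at SD 1 cm) the benefit is mainly in attributing the error. The attenuation, output error, depth, SD, number of settings and split are all assumptions. The change is worth making because it is nearly free, not because the pilot would otherwise fail.

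**What to change.** Add to section 8.2: *The signed deviation of each patient will be plotted against tube voltage, log(mAs) and measured AP depth, with simple slopes or differences between settings and 95% confidence intervals, reported as exploratory and read together.*

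Enter the exposure factors used to run the model as columns in the Excel sheet, and state where they are taken from, since section 7.1 does not list them. The plot against measured depth is needed because mAs may track patient size.

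Do not add a rule to section 2.1.2 barring correction from the pooled mean alone. Where the error really is a uniform offset, the pooled mean is a proper basis for correcting it.

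The cost is a sentence or two and a few spreadsheet columns, with no additional patients, procedures or exposure. The downside is limited precision: with 20 patients only strong associations (correlation about 0.59 or more for 80% power) are likely to be detected, and an association with mAs would guide further work without proving which value is wrong.

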## **2.2 OUTCOMES**

### **2.2.1 Primary Outcomes**

A measure of the accuracy with which the computational model estimates the anterior-posterior depth of patients undergoing abdominal x-ray examinations.

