[figure not shown]
The anonymised patient's x-ray image will be removed directly from the x-ray equipment using an NHS password protected USB memory stick. During this transfer, the software on the x-ray equipment will anonymise the image. This process has been checked using test

patients – the anonymisation process is complete – no patient identifiable information will be left on the image or within the electronic header.

The image will be transferred from the USB memory stick to an NHS Tayside password protected computer. From there, the necessary measurements will be made to allow the computational model to be used to estimate the patient's AP abdomen depth. This estimate will be compared to the physical measurement of AP abdomen depth made for the corresponding patient as recorded on the patient study form – this will determine the accuracy of the estimate.

There is no need for any patient follow up. Individual patients will only participate in the trial once. As this is a pilot study, 20 patients will be recruited in total. This will be enough as an initial cohort to determine whether the computational model is accurate enough to merit further clinical investigation, or if it is in need of adjustment.

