### 4. STUDY POPULATION

#### 4.1 NUMBER OF PARTICIPANTS

As this is a pilot study, 20 patients will be required after any drop outs. This will be enough as an initial cohort to determine whether the computational model is accurate enough to merit

further clinical investigation, or if it is in need of adjustment. It would be prudent to aim for an even male/female split.

As there is no patient follow-up, the patient's trial recruitment ends when they leave the Radiology department having had their abdomen x-ray examination.

If any participant chooses to withdraw from the study after their x-ray examination, their data will be deleted from the study database. These participants will be replaced to ensure 20 participants overall.

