## **8. STATISTICS AND DATA ANALYSIS**

### **8.1 SAMPLE SIZE CALCULATION**

The sample size for this pilot study will be 20 patients. There is no statistical aim or calculation in deriving this number; 20 is simply a high enough number as to allow for confidence in the computational model where all or most results are found to be individually accurate.

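### The only formal analysis in section 8.2 is a t-test for mean bias, which cannot show whether the model is accurate enough; no acceptable error, limits of agreement or confidence interval is planned

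*Combined protocol and SAP*

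**What the plan says.** The protocol describes the study's purpose in terms of accuracy throughout.

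- Section 1.2: "This pilot study is necessary to determine if the computational model is accurate enough to be relied upon".
- Section 2.1.1: "Accuracy will be determined by comparing this result with an actual measurement" of abdominal depth.
- Section 2.2.1 defines the primary outcome as "A measure of the accuracy with which the computational model estimates the anterior-posterior depth of patients undergoing abdominal x-ray examinations". It names no metric.
- Section 3.1 says that 20 patients are enough "to determine whether the computational model is accurate enough to merit further clinical investigation", the alternative being that the model needs adjusting. Section 4.1 repeats this.
- Section 8.1 disclaims any calculation for the sample size. It rests confidence in the model on the case "where all or most results are found to be individually accurate".

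Section 8.2 then gives the analysis. Each participant's predicted-minus-measured difference becomes a percentage, and the 20 values are summarised by "average, median, minimum and maximum deviations". Finally, "A t-test will be used to compare predicted and measured results".

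Sections 2.1.2 and 2.2.2 add a secondary aim: systematic error, if found, may be used to improve the model.

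**The concern.** A t-test asks whether the mean difference is distinguishable from zero. That suits the secondary aim, but it does not say how far the estimate for an individual patient may be from the truth. It scales the mean by the scatter, so a noisier model is less likely to be flagged for the same bias.

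The descriptive summaries are closer to the question, but they come with no statement of uncertainty and no benchmark. Neither 'individually accurate' nor 'most' is given a number. The plan also leaves open whether deviations are signed or absolute, what the percentage is a percentage of, and whether the t-test is paired (the per-participant differences imply that it is).

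At stake is the one decision the study exists to make: further investigation or adjustment. If the tolerance and the count are chosen after the errors have been seen, the same 20 results can support either verdict.

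**Working it through.** **Inputs.** From the documents: n = 20 (sections 3.1, 4.1 and 8.1), the percentage difference per patient and the t-test (section 8.2). The documents give no bias, SD, tolerance or alpha, and no calculation behind n = 20, so there is no stated figure to reproduce. Assumed for illustration: normal percentage errors, a paired two-sided test at 0.05, and the bias, SD, tolerance and count values shown.

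**1. What the t-test responds to.** It is significant when |mean difference| > t(0.975, 19) × SD/√20 = 2.093/4.472 × SD = 0.468 SD. Power comes from the noncentral t with 19 df. The share of patients within ±10% is Φ((10 − bias)/SD) − Φ((−10 − bias)/SD).

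| Bias | SD | Chance of significance | Patients within ±10% |
|---|---|---|---|
| 0 | 15% | 5.0% | 2Φ(0.667) − 1 = 49.5% |
| 2% | 2% | 98.9% | Φ(4) − Φ(−6) = 99.997% |
| 5% | 20% | 19% | 37% |

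The precise model is almost always flagged, and the two scattered models usually are not. The planned extremes would show the contrast descriptively. The expected maximum of 20 standard normals is 1.867, so signed extremes average about ±1.867 × 15 = ±28% for the first row and 2 ± 1.867 × 2, or −1.7% to +5.7%, for the second. Nothing in the plan says which of these is acceptable.

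**2. What the unset criterion does.** Take no bias and SD 10%. The probability that one patient is within tolerance is p = 2Φ(tolerance/10) − 1, and the number within tolerance is binomial(20, p).

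| Tolerance | p | Expected of 20 | P(at least 15 of 20) |
|---|---|---|---|
| ±5% | 0.383 | 7.7 | 0.1% |
| ±10% | 0.683 | 13.7 | 35% |
| ±15% | 0.866 | 17.3 | 96% |
| ±20% | 0.954 | 19.1 | >99.9% |

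At ±10%, moving the meaning of 'most' changes the chance of passing from 93% (at least 11) to 35% (at least 15) to 2.5% (at least 18).

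**3. What limits of agreement add over minimum and maximum.**

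- The signed minimum-to-maximum range of 20 values covers a further patient with average probability 19/21 = 90.5%. Its coverage follows Beta(19, 2), with 5th percentile 78%.
- Mean ± 1.96 SD covers on average 2·T₁₉(1.96/√1.05) − 1 = 92.9% under normality. The 5th percentile of its coverage is 84% by simulation.

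The gain in coverage is modest.

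**4. Precision available at n = 20.**

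- The 95% CI for mean bias is ±0.468 SD.
- The standard error of each limit of agreement is √(1/20 + 1.96²/(2 × 19)) = 0.389 SD, so its 95% CI is about ±2.093 × 0.389 = ±0.81 SD.
- Exact (Clopper-Pearson) 95% CIs for the proportion within tolerance are 83–100% for 20/20, 68–99% for 18/20, 51–91% for 15/20 and 32–77% for 11/20.

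**The case against.** The strongest reply is that the plan never makes the t-test the decision rule. It comes last in section 8.2, after the per-patient differences and their summaries; section 8.1 looks to individual results, and nowhere is non-significance equated with accuracy. The minimum and maximum do show spread, and without assuming normality. SD, limits of agreement and intervals could be computed later from the stored pairs. Every bias, SD and tolerance used above is assumed. This is a one-visit pilot that does not alter the patient's examination, and both of its possible outcomes lead to more work. Finally, the reference is a single reading from an in-house device, so limits of agreement would mix device error with model error.

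Much of this stands. The t-test has a legitimate use for the secondary aim, the signed extremes are informative, the coverage gain is small, and the figures show sensitivity rather than predict this study's result. Mixing of device and model error is real, but it affects the planned percentage differences equally and should be acknowledged whichever summary is used.

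What the reply does not remove is the missing criterion. Pilot status explains the absence of a power calculation. It does not explain assigning these 20 patients a choice between further investigation and adjustment with no stated basis for making it. A criterion chosen after the data are seen cannot be made prospective.

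**Conclusion.** The concern holds, and the plan should be changed. The one formal analysis addresses the secondary aim and cannot answer the primary question. The descriptive summaries that bear on the primary question have no stated uncertainty and no threshold. The missing tolerance and count matter most: in the illustration with no bias and SD 10%, the chance of passing runs from 0.1% to over 99.9% as the tolerance moves from ±5% to ±20%. Those sizes rest on normal errors and assumed bias, SD and tolerance. That the t-test tracks mean bias rather than individual error, and that no criterion is set, does not depend on those assumptions.

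**What to change.** In section 8.2:

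- Define the primary accuracy measure as the signed percentage difference: predicted minus measured, divided by measured depth.
- Report its mean with 95% CI, its SD, and 95% limits of agreement (mean ± 1.96 SD) with their 95% CIs. Add the median and maximum absolute percentage error. The planned signed minimum and maximum can stay.
- Before data collection, have the investigators state and justify an acceptable percentage error and how many of 20 count as 'most'. The documents offer no basis for either, so both must come from the intended use of the estimate. Report the number within that error with an exact 95% CI.
- Describe the t-test as paired, with its alpha and sidedness, and confine it to systematic bias under the secondary objective. State that non-significance is not evidence of accuracy.
- Note that the differences include error in the physical measurement.

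The cost is a wording change and two numbers agreed in advance. The same 20 pairs, Excel and SPSS suffice. The drawback is wide intervals: even 20 of 20 within tolerance leaves a lower bound of 83%, and each limit of agreement is known only to about ±0.81 SD.
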